The surveys are a novel series of questionnaires using previously validated tools such as the COPD Assessment Test or CAT (Jones PW, Harding G, Berry P et al 2009) and the Brief Pain Inventory (BPI) in order to subjectively assess each patient's own breathing/ respiratory and pain symptoms. The surveys also have additional questions gaging their pain medication usage, compliance with their treatment therapies (including IS and rib belt usage, when applicable). The survey is designed to be completed in ten minutes. The survey was constructed with the assistance of a professor psychologist who specializes survey construction (Author [name]). There will be no financial compensation for survey completions.

All surveys will be adapted to apply to the unique population being surveyed- the post-trauma population. This may involve removal of some questions that are not applicable to the rib fracture patients. There are several questions on the questionnaire that might not be applicable to the control group- they are simply instructed to not complete those four questions.

The surveys have been modified in order to be more easily comprehended to the average patient, and to require minimal additional instruction (so that the patient can complete them independently with no additional prompting).

The surveys that will be utilized are attached to the research protocol (see supplemental documents- Questionnaires 1,2, and 3).

Statistical Considerations: *Delineate the precise outcomes to be measured and analyzed. Describe how these results will be measured and statistically analyzed. Delineate methods used to estimate the required number of subjects. Describe power calculations if the study involves comparisons. Perform this analysis on each of the primary and secondary objectives, if possible.*

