In this study, we will utilize a quasi-experimental design to compare 35 subjects to themselves in a pre-test, post-test fashion. In addition, we will have an additional 15 non-interventional control patients to observe for temporal changes in patient's symptoms not secondary to the intervention itself. However, it is important to note that the study is not powered to detect differences between the control group and the intervention group. The purpose of the control group is to observe for differences that occur in this population over time regardless of intervention (it should be assumed that pain will improve as time increases from the set injury point, regardless of intervention). Further, this preliminary data could potentially be used to calculate an accurate power calculation for a definitive randomized controlled trial.

Groups will be compared by demographical and clinical data to determine what potentially confounding differences exist between the arms of the study. Relevant objective data that will be used to determine group differences include (but not limited to): age, sex, tobacco use status (active/former/none), presence of asthma, presence of COPD, or presence of restrictive lung

disease, home oxygen use, obstructive sleep apnea/ CPAP use, chronic pain incidence, narcotic/opioid medication consumption, obesity/ BMI. We will also measure relevant variables of their clinical course such as regional block/anesthesia/epidural administration. Radiological appearance of presenting imaging (either CT Chest or chest X-ray) will be compared by a dedicated and blinded radiologist who will grade the initial imaging based on severity including the following variables: number of fractures, bilateral vs. unilateral, degree of displacement, presence of lung contusion, presence of pneumothorax, presence of intrinsic lung disease, pleural effusion or blood.

Survey results (both pretest and posttests) will be compared using the appropriate statistical methods depending on the questions construct: with Chi squared performed for categorical variables (such as multiple choice) and unpaired t test for continuous variables (such as likert scale rankings).

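### The survey analysis is set out question by question: no pain or breathing score, no primary survey score and no primary time point are defined

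*Combined protocol and SAP*

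**What the plan says.** The only analysis rule for the questionnaires is in Statistical Considerations. Survey results are to be "compared using the appropriate statistical methods depending on the questions construct: with Chi squared performed for categorical variables (such as multiple choice", and an "unpaired t test for continuous variables (such as likert scale rankings".

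The Procedures section on surveys describes the instrument: "The surveys are a novel series of questionnaires using previously validated tools such as the COPD Assessment Test or CAT", together with "the Brief Pain Inventory (BPI) in order to subjectively assess each patient's own breathing/ respiratory and pain symptoms". It adds questions on medication use and compliance. On adapting the tools to trauma patients it says "This may involve removal of some questions that are not applicable to the rib fracture patients". Some questions may not apply to controls, and "they are simply instructed to not complete those four questions".

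The questionnaires are given three times, once before and twice after. They are described as essentially the same, with small changes to the first two questions, and are said to be attached. The primary objective lists questionnaires beside pain scores and narcotic consumption.

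No visible section defines a total or subscale score, a primary survey question, a primary post-test or a rule for multiple tests. The only score-level quantity is the MPQ PRI in the power calculation, and MPQ is not named among the survey tools.

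**The concern.** A rule that picks a test from the form of each question makes every pain and breathing question a separate comparison at each post-test. This has two consequences.

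- **Precision.** A single question is noisier than the average of several questions on the same symptom. Testing questions singly gives up information that patients have already supplied.
- **Interpretation.** A scatter of single-question p-values does not say whether pain or breathing improved, and each further question is another chance of a nominally significant result when belt and control patients are compared.

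The Purpose section frames success as a statistically significant improvement in pain control without significant respiratory impairment. Statistical Considerations also hopes to use the data to plan a definitive randomised trial. Both uses need a defined score with a known standard deviation.

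**Working it through.** **1. The plan's own power figure.** Inputs from Statistical Considerations: MPQ PRI mean 28, SD 16, a 20% decrease, within-subject correlation 0.8, two-sided alpha 0.05.

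- Difference: 0.20 × 28 = 5.6.
- SD of change: 16 × √(2 × (1 − 0.8)) = 10.12.
- Standardised effect: 5.6 / 10.12 = 0.553.
- Paired t test (noncentral t): 83.4% at n=30 (stated 83%) and 88.9% at n=35 (stated 88%).

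The figure reproduces to within a point. It is the power of one total score, tested once at 5%. It does not carry over to separate questions.

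**2. Precision.** Assume k items with equal SD, equal effect and common correlation r. The SD of their mean, relative to one item, is √((1 + (k − 1)r)/k), and the standardised effect rises by the reciprocal. For k = 4 (an assumption):

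| r | relative SD | gain in effect | equivalent gain in patients |
|---|---|---|---|
| 0.4 | 0.742 | 1.35 | 1.8 |
| 0.5 | 0.791 | 1.26 | 1.6 |
| 0.6 | 0.837 | 1.20 | 1.4 |

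As an illustration, suppose a four-item score had the planned effect of 0.553, hence 88.9% power at n=35 in a paired analysis. One of its items would then have an effect of 0.553 × 0.742 = 0.410 to 0.553 × 0.837 = 0.463, and power of 66% to 76%.

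**3. Chance findings, belt versus control.** The documents give no item count. Assume 8 to 15 efficacy questions answered by both groups, at two post-tests: 16 to 30 tests at two-sided 5%, no true difference. The independent case is 1 − 0.95^m for any significant result and 1 − 0.975^m for one favouring the belt, where m is the number of tests. The others use equally correlated normal test statistics.

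| Tests | Test correlation | At least one p<0.05 | At least one favouring the belt |
|---|---|---|---|
| 16 | 0 | 56% | 33% |
| 16 | 0.5 | 37% | 19% |
| 30 | 0 | 79% | 53% |
| 30 | 0.4 | 59% | 30% |
| 30 | 0.5 | 51% | 25.5% |
| 30 | 0.6 | 42% | 21% |

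Independence is not credible for questions on the same symptom, and it would contradict the correlation used in step 2. The rows at 0.4 to 0.6 are the ones to read.

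**4. Where step 3 does not apply.** The principal comparison is pre versus post within the 35 belt patients. The plan assumes that pain falls over time regardless of intervention, so no change is not the relevant null there. The planned unpaired test on paired data would also reject far less than 5% of the time under no change: at n=35, by simulation, about 0.7% if the within-subject correlation is 0.5 and about 0.01% if it is 0.8.

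**The case against.** The strongest reply is that the plan matches tests to data types and nowhere forbids a score. Any scoring key would sit in the attached questionnaires, which were not available for this review. That stands: a reader might infer that the plan has rejected scale scores, and the documents do not show it. They show only that the visible text names item-level tests and no score.

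Three further readings go too far.

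- A reader might infer that a favourable item is likely even if the belt does nothing. At correlations of 0.4 to 0.6 and 30 tests the chance is 21% to 30%. That is material, but it is not likely.
- A reader might apply the chance-finding figures to the within-patient comparison. Step 4 shows why they do not fit. The belt-versus-control comparison, which they do fit, is expressly unpowered and serves to show change over time.
- A reader might see the sentence on removing questions as room for selecting items after the data. In context it describes adapting the instrument. The surveys are said to be already modified, essentially the same at each time and attached. The protocol calls them novel and applies the word validated only to the source tools.

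It is also fair that this is a pilot with a quality-improvement aim, and that pain scores and narcotic use share the primary objective. That limits the weight of the point. It does not remove it, because the questionnaires are in that objective and significance is part of the stated hypothesis.

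**Conclusion.** The point holds in a limited form. The visible plan sets survey tests by question and leaves pain and breathing scores, a primary survey score and a primary time point undefined. Under the four-item assumption in step 2, item-level testing forgoes a 20% to 35% gain in standardised effect. In belt-versus-control comparisons, at test correlation 0.5, at least one nominally significant result would appear in about 37% (8 questions) to 51% (15 questions) of trials under no difference, and at least one favouring the belt in about 19% to 25.5%. Item counts and correlations are assumptions, so these sizes are illustrative. The gap in specification does not depend on them. It should be corrected, but it does not by itself undermine the study.

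**What to change.** In Statistical Considerations:

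- Define one pain score and one breathing score from the pain and breathing items common to all three attached questionnaires, and state how each is calculated. Questions that change between questionnaires, or that controls skip, stay out of the scores.
- Name one primary survey score and one primary post-test. This leaves a single primary survey test at 5%. Merely replacing items by, say, three scores at two post-tests would still leave six tests, with a 19% to 26% chance of at least one false positive (test correlation 0.6 to 0).
- Report single questions and the other time point descriptively.
- State that scores from adapted tools are not comparable with published totals.

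The cost is a paragraph, with no added patients, visits or questions, and the loss of comparability just noted. The change does not separate a belt effect from natural recovery in the pre-post comparison. The use of an unpaired test for pre-post data in the same patients is a separate matter that can be corrected in the same edit.

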Risks/Benefits: Describe any potential or known risks. This includes physical, psychological, social, legal or other risks. Estimate the probability that given risk may occur, its severity and potential reversibility. If the study involves a placebo or washout period, the risks related to these must be addressed in both the protocol and consent. Describe the planned procedures for protecting against or minimizing potential risks and assess their likely effectiveness. Where appropriate, discuss plans for ensuring necessary medical or professional intervention in the event of adverse effects to the subjects. Discuss the potential benefits of the research to the subjects and others. Discuss why the risks to the subjects are reasonable in relation to the anticipated benefits to subjects and others. Discuss the importance of the knowledge gained or to be gained as a result of the proposed research and why the risks are reasonable in relation to the knowledge that reasonably may result. If there are no benefits state so.

Theoretical risks to the use of the RibFx belt include worsening of pain or respiratory status. Risks are expected to be very low based on available clinical data regarding prior use of rib belts, and these devices are considered low risk by the FDA (class I device).

There is also a small potential risk given the nature of the study that a patient's protected health information (PHI) may be compromised during the study process, resulting in loss of confidentiality. For this reason we have implemented protocols to safeguard patient data to the maximum extent possible (see Data and Safety Monitoring, below).

Therapeutic Alternatives: List the therapeutic alternatives that are reasonably available that may be of benefit to the potential subject and include in the consent form as well.

Not Applicable

Therapeutic alternatives include pharmacological pain management (including narcotic and non-narcotic pain medications), local nerve blocks (including intercostal and epidural injections/catheters), and operative intervention (rib fixation).

Importantly, patients who receive our current intervention will receive all current therapeutic alternatives in addition (as the current modalities represent the standard of care, which they will still receive during the trial). The intervention planned (RibFx belt) will therefore be in addition to (rather than in lieu of) current therapeutic alternatives.

Patients deemed to be candidates for operative intervention (open rib fixation with or without thoracotomy/decortication), for reasons already stated elsewhere in the protocol, will not be including within the trial.

Data Safety and Monitoring: The specific design of a Data and Safety Monitoring Plan (DSMP) for a protocol may vary extensively depending on the potential risks, size, and complexity of the research study. For a minimal risk study, a DSMP could be as simple as a description of the Principal Investigator's plan for monitoring the data and performance of safety reviews or it could be as complex as the initiation of an external, independent Data Safety and Monitoring Board (DSMB). The UVM/UVM Medical Center process for review of adverse events should be included in the DSMP.

Data safety and monitoring will be the responsibility of the entire research team, however ultimate responsibility for safeguarding the patient's data will fall on the primary investigator. While 100% security of such data is never fully possible, the research team commits to taking all necessary and reasonable steps toward protecting patient data from HIPAA violation.

All the patient data will be kept in secure locations. When electronic, this involves storing the files only on secure servers with password protection. When in physical/paper copies, this involves use of lock-and-key filing cabinets and offices. All aggregate data will be coded to remove patient identifiers, as able, to safeguard the security of their identifiable data.

Adverse Event and Unanticipated Problem (UAP) Reporting: Describe how events and UAPs will be evaluated and reported to the IRB. All protocols should specify that, in the absence of more stringent reporting requirements, the guidelines established in the Committees on Human Research "Adverse Event and Unanticipated Problems Reporting Policy" will be followed. The UVM/UVM Medical Center process for review of adverse events and UAPs to subjects or others should be included in the DSMP.

Adverse events will be reported as soon as they are identified to the research protections office and will be subject to thorough review. The affected patients, if applicable, will be notified regarding this adverse event. If needed, the clinical care team will provide any medical care related to this adverse event. Necessary changes to prevent the recurrence of such an event will be implemented with the assistance of the review board, and if necessary (for serious adverse events) the trial may be terminated early for patient safety.

Withdrawal Procedures: Define the precise criteria for withdrawing subjects from the study. Include a description of study requirements for when a subject withdraws him or herself from the study (if applicable).

Patients will be eligible to withdraw from the study at any time if they chose to. This includes participants in both the control and intervention arms of the trial. Subjects will be asked to provide a reason for withdrawal (such as intolerance or difficulty with the rib belt, worsened pain associated with the rib belt, personal preference, difficulty complying with study rules, etc.), but patients are also free to withdraw without providing a reason.

A patient may be deemed no longer eligible for inclusion in the trial by the research team (such as if the patient undergoes rib fixation surgery). These patients will be removed from the trial and will be notified of the reason for their removal.

Sources of Materials: Identify sources of research material obtained from individually identifiable human subjects in the form of specimens, records or data. Indicate whether the material or data will be obtained specifically for research purposes or whether use will be made of existing specimens, records or data.

Sources of materials will principally be derived from studies, images, tests that the patient is already undergoing as part of the standard of care for rib fracture treatment. The only additional test obtained solely for research purposes is the pre-test and post-test questionnaires. X-rays and imaging tests analyzed will be obtained for clinical use and NOT solely for research purposes, however the images will undergo additional analysis by a blinded radiologist participating in the study. This will not incur any additional costs or radiation to the patient.

DRUG AND DEVICE INFORMATION

Investigators are encouraged to consult the UVM Medical Center Investigational Pharmacy Drug Service ([name]) prior to finalizing study drug/substance procedures.

Drug (s)

Not applicable

Drug name – generic followed by brand name and common abbreviations. Availability – Source and pharmacology; vial or product sizes and supplier. If a placebo will be used, identify its contents and source. (attach investigational drug brochure)

N/A

Preparation: Reconstitution instructions; preparation of a sterile product, compounded dosage form; mixing guidelines, including fluid and volume required. Identify who will prepare.

N/A

Storage and stability – for both intact and mixed products.

N/A

Administration – Describe acceptable routes and methods of administration and any associated risks of administration.

N/A

Toxicity – Accurate but concise listings of major toxicities. Rare toxicities, which may be severe, should be included by indicated incidence. Also adverse interactions with other drugs used in the protocol regimen as well as specific foods should be noted. Address significant drug or drug/food interactions in the consent form as well. List all with above details.

N/A

Is it FDA approved: (include FDA IND Number)

1. in the dosage form specified? If no, provide justification for proposed use and source of the study drug in that form.

N/A

2. for the route of administration specified? If no, provide justification for route and describe the method to accomplish.

N/A

3. for the intended action?

N/A

Device (s)

Not applicable

Device name and indications (attach investigational device brochure)

RibFx Rib Orthosis Belt (PelvicBinder, Inc.)

Is it FDA approved: (include FDA IDE Number)

1. for indication specified? If no, provide justification for proposed use and source of the device.

The device is exempt from FDA approval as a Class I Medical Device

Risk assessment (non-significant/significant risk) - PI or sponsor needs to assess risk of a device based upon the use of the device with human subjects in a research environment.

Non-significant risk to humans in a monitored research environment.

SUBJECT CHARACTERISTICS, IDENTIFICATION AND RECRUITMENT

Subject Selection: Provide rationale for subject selection in terms of the scientific objectives and proposed study design.

Subjects targeted for the study are those that would benefit most from the intervention (Rib belt)- patients with traumatic rib fractures. In order to determine if the belt has efficacy in this population, we must utilize the belt in this target population. Patients at the extremes of age (<18 or >80 years old) have been ruled out as they may create unreasonable confounding when measuring the relevant study outcomes, as well as potentially creating issues with autonomy and consent processes. There are also other exclusion criteria as dictated below.

Vulnerable Populations: Explain the rationale for involvement of special classes of subjects, if any. Discuss what procedures or practices will be used in the protocol to minimize their susceptibility to undue influences and unnecessary risk (physical, psychological, etc.).

Not applicable

Number of Subjects: What is the anticipated number of subjects to be enrolled at UVM/UVM Medical Center and in the case of a multi-center study, with UVM/UVM Medical Center as the lead, the total number of subjects for the entire study.

The current anticipated number of subjects is 35 patients in the intervention arm, and 15 in the control arm of the study, for a total of 50 patients. All these subjects will be enrolled at UVMMC.

Inclusion/Exclusion Criteria: Eligibility and ineligibility criteria should be specific. Describe how eligibility will be determined and by whom. Changes to the eligibility criteria at a later phase of the research have the potential to invalidate the research.

Inclusion Criteria:

Adult person age 18-80 admitted with at least one acute traumatic closed rib fracture to the University of Vermont Medical Center

Exclusion Criteria:

Pediatric (<18 year old) and Geriatric (>80 year old) patients

Patients who are intubated on arrival or within first 24 hours of admission or with Glasgow Coma Scale (GCS) < 14 (altered or depressed consciousness)

Pregnant patients

Patients who undergo operative rib fixation for their rib fractures (such as open reduction internal fixation, or rib plating)
 Patients with chest wall deformity, lacerations, burns, or soft tissue injuries that preclude placement of the RibFx belt
 Patients with an additional mechanism of injury that would create severe distracting pain, as determined by the admitting team.
 Isolated 1st rib or 2nd rib fractures

Inclusion of Minorities and Women: Describe efforts to include minorities and women. If either minorities or women are excluded, include a justification for the exclusion.

The inclusion criteria make no specification for inclusion or exclusion from the study in regards to race, gender, religion, or sexual orientation. All groups will be included in the study if they wish to enroll and meet the otherwise laid out clinical criteria (see exclusion criteria above).

Inclusion of Children: Describe efforts to include children. Inclusion is required unless a clear and compelling rationale shows that inclusion is inappropriate with respect to the health of the subjects or that inclusion is inappropriate for the purpose of the study. If children are included, the description of the plan should include a rationale for selecting or excluding a specific age range of children. When included, the plan must also describe the expertise of the investigative team in working with children, the appropriateness of the available facilities to accommodate children, and the inclusion of a sufficient number of children to contribute to a meaningful analysis relative to the purpose of the study. If children are excluded then provide appropriate justification. Provide target accrual for this population.

Due to concerns regarding potential size-match criteria for the RibFx medical device, as well as issues with the consent process, we have elected not to include children into the study population. As stated in the exclusion criteria, those less than 18 years of age will not be offered to participate in the trial.

For protocols including the use of an investigational drug, indicate whether women of childbearing potential have been included and, if not, include appropriate justification.

N/A

If HIV testing is included specifically for research purposes explain how the test results will be protected against unauthorized disclosure. Include if the subjects are to be informed of the test results. If yes, include the process and provision for counseling. If no, a rationale for not informing the subjects should be included.

Not applicable

Recruitment: Describe plans for identifying and recruitment of subjects. All recruitment materials (flyers, ads, letters, etc.) need to be IRB approved prior to use.

Patients who are first identified by the clinical care team (The Acute Care Surgery/ACS/ Trauma Surgery team at UVMC) as meeting the desired inclusion criteria for the trial will be offered the opportunity to participate in the trial and appropriate clinical materials will be given by a member of the research team. There will be no advertisements, mailers, or other relevant recruitment materials other than an informational pamphlet, a device pamphlet, and the appropriate consent/authorization forms. These items are attached with the relevant research forms.

FINANCIAL CONSIDERATIONS

Expense to Subject: If the investigation involves the possibility of added expense to the subject (longer hospitalization, extra studies, etc.) indicate in detail how this will be handled. In cases where the FDA has authorized the drug or device company to charge the patient for the experimental drug or device, a copy of the authorization letter from the FDA or sponsor must accompany the application. Final approval will not be granted until the IRB receives this documentation.

There are very limited circumstances under which study participants may be responsible (either directly or via their insurance) for covering some study-related expenses. If the study participant or their insurer(s) will be billed for any portion of the research study, provide a justification as to why this is appropriate and acceptable. For example, if the study involves treatment that is documented standard of care and not investigational, state so. In these cases, the protocol and the consent should clearly define what is standard of care and what is research.

The research team does not anticipate that participation in the trial will result in any additional hospital time or expense. The actual RibFx belt will be provided, free of charge to the patient (actual retail value \$125 USD). All other interventions and modalities will be per the current standard of care for the treatment of rib fractures- patients will continue to be billed for the rest of their hospital care. In that (expectedly) extreme rare event that at any point during the trial it became apparent that the device has caused a medical complication necessitating additional treatment, this medical care will be provided without billing the patient for those services.

Payment for participation: Describe all plans to pay subjects, either in cash, a gift or gift certificate. Please note that all payments must be prorated throughout the life of the study. The IRB will not approve a study where there is only a lump sum payment at the end of the study because this can be considered coercive. The amount of payment must be justified. Clarify if subjects will be reimbursed for travel or other expenses.

Not applicable

There will be no payment or financial incentive for the subjects to participate. The medical device RibFx belt will be provided to the intervention group free of charge, and they will be allowed to keep the medical device upon discharge (MSRP \$125 USD).

Collaborating Sites. When research involving human subjects will take place at collaborating sites or other performance sites when UVM/UVM Medical Center is the lead site, the principal investigator must provide in this section a list of the collaborating sites and their Federalwide Assurance numbers when applicable. (agreements may be necessary)

Not applicable

Single center study at the University of Vermont Medical Center main campus (Burlington, VT). No collaborating centers or satellite/off-site locations.

INFORMED CONSENT

Consent Procedures: Describe the consent procedures to be followed, including the circumstances under which consent will be obtained, who will seek it, and the methods of documenting consent. Specify the form(s) that will be used e.g. consent (if multiple forms explain and place identifier on each form), assent form and/or HIPAA authorization (if PHI is included). These form(s) must accompany the protocol as an appendix or attachment.

Note: Only those individuals authorized to solicit consent may sign the consent form confirming that the prospective subject was provided the necessary information and that any questions asked were answered.

Consent will be obtained at the time of enrollment (during the first 24 hours of the patient's inpatient admission/observation, on their initial encounter for acute traumatic rib fracture) and consent will be obtained at the bedside by one of the members of the research team.

All documentation of consent observation/supervision will be kept in the study regulatory binder.

After verbally explaining the rational, reasoning, risks, and potential benefits of the study, patients will have ample opportunity to decide whether or not to enroll without feeling pressured into enrolling (up to 24 hours will be permitted for deciding). Relevant written materials will be left for further review, including a written consent form, device pamphlet, and information pamphlet (All included in the IRB materials). Upon request of the patient, a member of the research team will always be available to answer further questions regarding the study via a "hot line" and also via the clinical care team.

Information Withheld From Subjects: Will any information about the research purpose and design be withheld from potential or participating subjects? If so, explain and justify the non-disclosure and describe plans for post-study debriefing.

Not applicable

No information will be withheld from subjects. N/A

Attach full grant application, including budget information and/or any contract or draft contract associated with this application.

All materials must be submitted electronically to the IRB via InfoEd. Proper security access is needed to make electronic submissions. Visit the [InfoEd Resource Materials](#) page for more information.
